8.3.8 Dose Modifications for Pulmonary Toxicity

- **Grade 2 or 3 pneumonitis:** Interrupt everolimus until \leq grade 1. Resume everolimus at one dose level decreased
- **Grade 4 pneumonitis:** Discontinue everolimus

8.3.9 Dose Modifications for Renal Toxicity

- **Grade 2 increased creatinine:** Interrupt everolimus until grade ≤ 1 , then resume with one dose level decreased
- **Grade 3 and 4 increased creatinine:** Discontinue everolimus

8.3.10 Dose Modifications for Metabolism

Grade 4 Hyperglycemia: Interrupt everolimus until grade ≤ 2 , then resume at same dose

8.3.11 Dose Modifications for General Disorders

Grade 3 Edema: Interrupt everolimus until \leq grade 2, then resume at one dose level decreased

8.3.12 Dose Modifications for Other Non-hematologic Toxicities

For other clinically significant grade 3/4 non-hematologic toxicities likely related to sorafenib or everolimus, interrupt sorafenib or everolimus. Resume sorafenib or everolimus at 1 dose level reduced when the toxicity resolves to a clinically acceptable level (grade 1/2).

8.4 Dose Modifications for Everolimus alone (after crossover)

- If multiple adverse events are seen, administer dose based on greatest reduction required for any single adverse event observed. Reductions or increases apply to treatment given in the preceding cycle and are based on adverse events observed since the prior dose.
- Everolimus will not be re-escalated once reduced
- If dose reductions beyond dose level -2 is required or everolimus is held for 4 weeks, everolimus will be discontinued.
- If more than one of these toxicities apply, use the most stringent criteria (i.e., the greatest dose reduction.).

CTEP-AERS reporting may be required for some adverse events (See [Section 9.0](#))

8.4.1 Dose levels

Dose reduction of everolimus will be performed according to the table below. Everolimus will be permanently discontinued for patients who require dose interruptions of > 28 days or who experience dose limiting toxicities at dose level -2. Missed doses of everolimus will not be made up.

Dose Level	Drug Name	Dose
0*	Everolimus	10mg daily
-1	Everolimus	5mg daily
-2	Everolimus	2.5mg daily

*Dose level 0 refers to the starting dose.

8.4.2 Dose Modifications for Hematologic Toxicities

Grade ≥ 3 neutropenia, thrombocytopenia, or neutropenic fever: Interrupt everolimus until \leq grade 2, then resume with one dose level reduction of everolimus for all subsequent doses.

8.4.3 Dose Modifications for Gastrointestinal Toxicities

- **Grade ≥ 3 diarrhea:** Interrupt everolimus until diarrhea improves to \leq grade 2, then resume everolimus with one dose level reduction.
- **Grade 3 stomatitis:** Interrupt everolimus until \leq grade 1 then resume with one dose level reduced.
- **Grade 4 stomatitis:** Discontinue everolimus

8.4.4 Dose Modifications for Hepatic Dysfunction

- **Grade 2 blood bilirubin increased:** Interrupt everolimus until improved to grade 1, then resume everolimus at same dose.
- **Grade 3 blood bilirubin increased:** Interrupt everolimus until improved to grade 1, then resume everolimus at 1 dose level reduced.
- **Grade 4 blood bilirubin increased:** Discontinue everolimus.
- **Grade 3 transaminase increased:** Interrupt everolimus until improved to grade 1, then resume everolimus at 1 dose level reduced.
- **Grade 4 transaminase increased:** Discontinue everolimus.

8.4.5 Dose Modifications for Skin Toxicity

- **Grade 4 Acneiform Rash:** Interrupt everolimus until grade \leq 2, then restart at one dose level decreased
- **Grade 3 Maculopapular Rash:** Interrupt everolimus until grade \leq 2, then restart at one dose level decreased

8.4.6 Dose Modifications for Pulmonary Toxicity

- **Grade 2 or 3 pneumonitis:** Interrupt everolimus until \leq grade 1. Resume everolimus at one dose level decreased

- **Grade 4 pneumonitis:** Discontinue everolimus

8.4.7 Dose Modifications for Renal Toxicity

- **Grade 2 increased creatinine:** Interrupt everolimus until grade ≤ 1 , then resume with one dose level decreased
- **Grade 3 and 4 increased creatinine:** Discontinue everolimus

8.4.8 Dose Modifications for Metabolism

Grade 4 Hyperglycemia: Interrupt everolimus until grade ≤ 2 , then resume at same dose

8.4.9 Dose Modifications for General Disorders

Grade 3 Edema: Interrupt everolimus until \leq grade 2, then resume at one dose level decreased

8.4.10 Dose Modifications for Other Non-hematologic Toxicities

For other clinically significant grade 3/4 non-hematologic toxicities likely related to everolimus, interrupt everolimus. Resume everolimus at 1 dose level reduced when the toxicity resolves to a clinically acceptable level (grade 1/2).

9.0 ADVERSE EVENTS

The prompt reporting of adverse events is the responsibility of each investigator engaged in clinical research, as required by Federal Regulations. Adverse events must be described and graded using the terminology and grading categories defined in the NCI's Common Terminology Criteria for Adverse Events (CTCAE), Version 4.0. However, CTCAE v5.0 must be used for serious AE reporting through CTEP-AERS as of April 1, 2018. The CTCAE is available at [REDACTED]. Attribution to protocol treatment for each adverse event must be determined by the investigator and reported on the required forms, using the codes provided.

9.1 Routine adverse event reporting

Adverse event data collection and reporting, which are required as part of every clinical trial are done to ensure the safety of patients enrolled in the studies as well as those who will enroll in future studies using similar agents. Adverse events are reported in a routine manner at scheduled times according to the study calendar in [Section 5.0](#). For this trial, Rave is used for routine AE reporting.

Solicited Adverse Events: The following adverse events are considered "expected" and their presence/absence should be solicited, and severity graded, at baseline and for each cycle of treatment.

CTCAE v4.0 Term	CTCAE v4.0 System Organ Class (SOC)
Neutrophil count decreased	Investigations
Platelet count decreased	Investigations
Hemoglobin decreased	Investigations
Hyperglycemia	Metabolism and nutrition disorders
Hypertension	Vascular disorders
Fatigue	General disorders
Palmar-plantar erythrodysesthesia syndrome	Skin and subcutaneous tissue disorders
Diarrhea	Gastrointestinal disorders
Weight Loss	Investigations

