1.2 Everolimus

Everolimus is an orally available inhibitor of the mammalian target of rapamycin (mTOR). Everolimus is a macrolide derivative of rapamycin, a natural compound produced by bacteria.

Everolimus has been formulated for oral administration, and is being developed as an anticancer agent and an immunosuppressant. Everolimus selectively inhibits mTOR, an evolutionarily-conserved intracellular serine/threonine kinase implicated in the control of protein translation^{1,2}.

Everolimus binds the intracellular 12-kilodalton immunophilin FK506-binding protein (FKBP12) with high affinity; the resulting FKBP12/everolimus complex then inhibits mTOR kinase activity. Phosphatidylinositol 3-kinase (PI3-K) and Akt are well described upstream regulators of mTOR activity, although other mechanisms of mTOR activation have been described. Two well-characterized phosphorylation targets of mTOR are eIF4E-binding protein (4E-BP1) and p70 S6 kinase 1 (S6K1), which regulate translation of proteins required for G1-S phase progression in the cell cycle. TOR inhibitors such as everolimus usually are cytostatic when administered alone, although anti-proliferative and pro-apoptotic effects also have been described^{1,2}.

At weekly and daily schedules and at various doses explored, everolimus is generally well tolerated. The most frequent adverse events (rash, mucositis, fatigue and headache) associated with everolimus therapy are manageable. Non-infectious pneumonitis has been reported with mTOR inhibitors but is commonly low-grade and reversible.

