1.3 Combination of sorafenib and temsirolimus/everolimus in cancers other than thyroid cancer

Preclinical evidence suggests synergy when both the MAPK and PI3K-mTOR pathways are inhibited³. The combination of sorafenib with mTORC1 inhibitors increases cell death in melanomas, where *BRAF* mutations are particularly common⁴, and the combination of sorafenib and temsirolimus was evaluated in the treatment of melanoma in a large randomized phase II study through the Southwest Oncology Group⁴⁴ and evaluated in the treatment of kidney cancer (by the Eastern Cooperative Oncology Group). It is currently being evaluated in the treatment of glioblastoma multiforme (North Central Cancer Treatment Group). In the phase I study evaluating sorafenib and temsirolimus (another mTOR inhibitor)⁵, a partial response was seen in a subject with papillary thyroid cancer. The combination of sorafenib and everolimus has been evaluated in a phase I study for kidney cancer, with the recommended dose of sorafenib 400 mg twice a day with everolimus 5 mg daily⁶. In the phase I study, treatment-related events that occurred greater than 20% of the time included diarrhea, hand-foot syndrome, hypertension, hypophosphatemia, hypothyroidism, and rash. Pharmacokinetic data suggested that everolimus had no effects on sorafenib blood levels. The most common grade 3 toxicity was hypophosphatemia (45%) as well as grade 3 diarrhea (10%). At the MTD, 75% of patients eventually required dose reduction (although this percentage is similar to what is seen with sorafenib alone in the DECISION study).

1.4 **Hürthle cell thyroid cancer**

Hürthle cell thyroid cancers in general have not been as well studied as other cell types. Evaluation of the SEER database confirms that cancer-specific survival is worse in this subgroup compared to other thyroid cancers³⁵. It accounts for about 4% of all thyroid cancers. Characteristically, they are large cells with hyperchromatic nuclei and an abundant granular cytoplasm containing large numbers of mitochondria.

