- C Thyrotropin (Thyroid Stimulating Hormone or TSH), Serum every 2 cycles (or every 8 weeks, +/- 2 weeks).
- D Every 2 cycles (or every 8 weeks, +/- 2 weeks) for the first 12 cycles. Every 2 cycles (or every 16 weeks, +/- 2 weeks) thereafter. This must include the minimum of the neck and chest CT scan at baseline, although an abdominal and pelvic CT scan are strongly recommended at baseline. Intravenous contrast should be given unless there is indication to omit; as documented by the treating physician. A MRI of the neck may be substituted for a CT of the neck. Documentation (radiologic and pathology report) of the diagnosis scan must be submitted. A PET/CT can be substituted if the index lesions can be measured appropriately per RECIST 1.1.
- E Adverse events should be collected Day 1 of every cycle beginning with cycle 3 until year 1. After 12 cycles (1 year) adverse events can be collected every other cycle.
- Σ Albumin, alkaline phosphatase, total bilirubin, bicarbonate, BUN, calcium, chloride, creatinine, glucose, potassium, total protein, SGOT[AST], SGPT[ALT], sodium, bilirubin.
- π All patients will have baseline lipid profile. Also, if it has been more than 3 months since the last lipid profile, it must be repeated at crossover. It is strongly recommended these patients have a lipid profile after 2 cycles, then every 4 cycles while on everolimus.
- Ψ For patients who have come off of treatment for progression, no further scans are needed. For patients who have come off treatment for any other reason, disease status information (i.e. progression status) will be collected every 3 months (+/- 1 month) until progression. It may be done more frequently as per the investigator. It no longer needs to be done if a patient begins other systemic treatment for the thyroid cancer. Documentation (radiologic) must be provided at progression of disease. In addition, survival and disease status information is required approximately every 6 months until 5 years after registration. This does not require that the subject be seen and/or examined. For example, follow-up may be done through a telephone call to the subject or his treating physician.

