9.2 CTCAE Routine Study Reporting Requirements

***Combinations of CTCAE Grade & Attribution Required for Routine AE Data Submission on Case Report Forms (CRFs)**

Attribution	Grade 1	Grade 2	Grade 3	Grade 4	Grade 5
Unrelated			a	a	a
Unlikely			a	a	a
Possible		a	a, b	a, b	a, b
Probable		a	a, b	a, b	a, b
Definite		a	a, b	a, b	a, b

- a) Adverse Events: Other CRF - Applies to AEs occurring between registration and within 30 days of the patient's last treatment date, or as part of the Clinical Follow-Up Phase.
- b) Adverse Events: Late CRF - Applies to AEs occurring greater than 30 days after the patient's last treatment date.

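### Serum phosphate is not on the scheduled panel and hypophosphatemia is not a solicited term, so grade 3 cases in either arm are recorded only if a site chooses to test

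*Combined protocol and SAP*

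**What the plan says.** **Solicited terms (Section 9.1).** Nine terms are listed: neutrophils, platelets, hemoglobin, hyperglycemia, hypertension, fatigue, palmar-plantar erythrodysesthesia, diarrhea and weight loss. The instruction is "and their presence/absence should be solicited, and severity graded, at baseline and for each cycle of treatment". Hypophosphatemia is not listed.

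**Serum panel (Section 5.0, footnote Σ).** The panel is "Albumin, alkaline phosphatase, total bilirubin, bicarbonate, BUN, calcium, chloride, creatinine, glucose, potassium, total protein, SGOT[AST], SGPT[ALT], sodium, bilirubin". Phosphate is absent. The panel is drawn before registration, on days 1 and 15 of cycles 1 and 2, on day 1 of each later cycle, and at post-treatment follow-up. The opening of Section 5.0 leaves laboratory follow-up during treatment to institutional guidelines and the physician's judgment.

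**Prior data (Section 1.3).** On the phase I study of sorafenib with everolimus in kidney cancer: "The most common grade 3 toxicity was hypophosphatemia (45%) as well as grade 3 diarrhea (10" (the quotation stops before the last per cent sign).

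**Risk lists (Section 9.4).** Hypophosphatemia is in the Likely (>20%) column for sorafenib and the Less Likely column for everolimus.

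**Routine reporting (Section 9.2).** Grade 3 to 5 events are required under every attribution. Grade 2 events are required if at least possibly related, and grade 1 events are not required. The form is described as "Adverse Events: Other CRF - Applies to AEs occurring between registration and within 30 days" of the last treatment date.

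**Analysis (Section 13.3).** Maximum grade is summarized for each type of event. Grade 3+ events are compared between arms by Chi-square or Fisher's exact test. Section 2.2 makes the comparison of adverse event rates part of the secondary objective.

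**The concern.** Hypophosphatemia is found by measuring phosphate. The protocol expects it often with the combination and also lists it as frequent with sorafenib alone, but schedules no measurement and puts no question about it on the form. A grade 3 case then enters the database only if a site orders the test on its own initiative.

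Three things are at stake:

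- The grade 3+ comparison could miss what may be the most common grade 3 event of the combination.
- Testing habits may vary by site and, since neither placebo nor blinding is described, by arm. A physician who knows the patient is taking everolimus may test more, or may not.
- Rules that act on graded toxicity, such as the rules for other non-hematologic toxicities (Sections 8.2.8 and 8.3.12) and the grade 4 criterion in Section 13.7, cannot count an event that was not measured. With no baseline value, a low result found later also cannot be separated from a pre-existing one.

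**Working it through.** **Step 1. The plan's own figures.** Section 13.4 inflates 30 evaluable patients by 10%: 30 / 0.90 = 33.3, rounded up to 34, or 17 per arm. This reproduces. The plan gives no power or precision figure for the adverse-event comparison, so there is nothing further to reproduce.

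**Step 2. Can any recording route capture an untested case?**

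| Route | Effect for hypophosphatemia |
|---|---|
| Scheduled panel (5.0, footnote Σ) | Phosphate not measured |
| Solicited list (9.1) | Term not prompted |
| Mandatory grade 3–5 reporting (9.2) | Applies only once the event is known |
| Nursing guidelines for sorafenib (10.1) | Name sodium, calcium and potassium disturbances and point to the chemistry panel, which lacks phosphate |
| Site discretion (opening of 5.0) | Captures the event if the site tests |

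Only the last route can find a case, and it is not a requirement.

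**Step 3. Number of patients at stake.** Apply the 45% from Section 1.3, assuming that it carries over to this population and dose:

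- 17 per arm: 0.45 × 17 = 7.65
- 15 per arm: 0.45 × 15 = 6.75

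Let c be the fraction of true grade 3 cases detected (assumed range 25% to 100%). Recorded cases among 17 combination patients are 7.65 × c: 7.65 at 100%, 3.8 at 50%, 1.9 at 25%.

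**Step 4. Effect on the arm comparison.** Let p be the grade 3 rate on sorafenib alone, assumed 5% to 30%. With equal capture in both arms, the recorded difference is c × (0.45 − p), so it shrinks in proportion to c. Exact power of Fisher's test with 17 per arm and two-sided 0.05 (assumed, since the plan states no level) is:

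| p (assumed) | c = 100% | c = 75% | c = 50% | c = 25% |
|---|---|---|---|---|
| 5% | 72% | 51% | 24% | 3% |
| 10% | 51% | 34% | 16% | 2% |
| 20% | 22% | 14% | 8% | 2% |
| 30% | 8% | 5% | 4% | 1% |

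With 15 per arm, power at full capture runs from 64% (p = 5%) to 6% (p = 30%). Power is modest even with full capture, so the main value of the fix is an honest count in each arm rather than a significant test.

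**Step 5. Direction if capture differs by arm.** The recorded difference is c₂ × 0.45 − c₁ × p, where c₂ is capture on the combination and c₁ on sorafenib alone. Take p = 20%, for a true difference of 25 points:

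- c₂ = 75%, c₁ = 25%: 0.3375 − 0.05 = 28.75 points (overstated)
- c₂ = c₁ = 50%: 0.225 − 0.10 = 12.5 points (understated)
- c₂ = 25%, c₁ = 75%: 0.1125 − 0.15 = −3.75 points (reversed)

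The sign of the bias depends on capture rates that the documents do not give.

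**The case against.** The strongest reply is that a short solicited list backed by mandatory grade-based reporting is a coherent design. Section 9.2 takes every grade 3 to 5 event under any attribution, and the planned test uses only grade 3+. The protocol mentions hypophosphatemia in several places, so sites are alerted and may well test. The 45% comes from a phase I kidney-cancer study; Section 1.3 gives no denominator and does not tie the figure to this trial's dose. The event is also frequent with sorafenib, so missing tests would affect both arms.

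Most of this stands, and it limits the point. It does not close the gap for hypophosphatemia, because mandatory reporting presupposes detection and detection here rests on an optional test.

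A reader might go further and infer that the main everolimus toxicities in general are under-recorded in the arm comparison. Section 1.2 says "The most frequent adverse events (rash, mucositis, fatigue and headache) associated with everolimus therapy are manageable" and also "Non-infectious pneumonitis has been reported with mTOR inhibitors but is commonly low-grade and reversible", yet oral mucositis, rash and pneumonitis are not solicited either. The documents do not support that inference, for three reasons:

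- Grade 3+ events of these three types are already mandatory on the form. What non-solicitation loses is grade 1, grade 2 judged unrelated or unlikely, and a prompted yes or no. That touches the maximum-grade summary and leaves the reporting requirement behind the grade 3+ test unchanged.
- These events are not left unattended. The nursing guidelines in Section 10.2 ask for pneumonitis symptoms to be assessed at each visit, and Sections 8.3.3, 8.3.7 and 8.3.8 have grade-specific rules for stomatitis, rash and pneumonitis.
- The list is not clearly tilted toward sorafenib. Seven of the nine solicited terms are on the everolimus possible-relationship list in Section 9.4.2 (all but hypertension and palmar-plantar erythrodysesthesia), and three of its five Likely terms are solicited (anemia, diarrhea, fatigue).

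**Conclusion.** The point holds for hypophosphatemia. It is the one event of those considered that can be missed at grade 3+ by design, in either arm. At 45%, 7 to 8 of 17 combination patients are at stake. The number actually missed could lie anywhere from none to all of them, because the documents give no capture rate.

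A reader might also infer that the plan understates the toxicity everolimus adds, or might put a figure on the shortfall in the overall grade 3+ rate. Neither is supported. The 45% is a combination rate and not an everolimus increment, and no sorafenib-alone grade 3 rate is given. A shortfall in the overall rate would need an assumed rate of other grade 3+ events, independence between events, and zero detection. None of these is in the documents, and zero detection is unlikely given site discretion.

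The conclusion rests on the panel and solicited list as printed and on Section 5.0 not requiring phosphate elsewhere. The counts also assume that the phase I rate carries over. The power figures assume a 5% to 30% sorafenib-alone rate, equal capture of 25% to 100%, and a two-sided 0.05 level. This is an inexpensive improvement to a secondary endpoint and to safety ascertainment. It does not affect the primary progression-free survival analysis.

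**What to change.** In Section 5.0, add phosphate to footnote Σ, so that it is measured at baseline and at every draw already scheduled for the panel, in both arms. In Section 9.1, add hypophosphatemia to the solicited terms for both arms. No dose or management rule needs to change for this purpose.

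The cost is one more analyte on a sample already taken and one more line on the adverse-event form per cycle.

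Soliciting oral mucositis, maculo-papular rash and pneumonitis as well is optional. It would add three more lines per cycle and would improve only the low-grade and prompted data behind the maximum-grade summary.

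If patients have already been treated when the change is made, the report should state how many in each arm had phosphate measured, and give the hypophosphatemia rate among those tested alongside the rate among all treated.

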9.2 CTCAE Routine Study Reporting Requirements

***Combinations of CTCAE Grade & Attribution Required for Routine AE Data Submission on Case Report Forms (CRFs)**

Attribution	Grade 1	Grade 2	Grade 3	Grade 4	Grade 5
Unrelated			a	a	a
Unlikely			a	a	a
Possible		a	a, b	a, b	a, b
Probable		a	a, b	a, b	a, b
Definite		a	a, b	a, b	a, b

- a) Adverse Events: Other CRF - Applies to AEs occurring between registration and within 30 days of the patient's last treatment date, or as part of the Clinical Follow-Up Phase.
- b) Adverse Events: Late CRF - Applies to AEs occurring greater than 30 days after the patient's last treatment date.

9.3 Expedited Adverse event reporting (CTEP-AERS)

Investigators are required by Federal Regulations to report serious adverse events as below. Alliance investigators are required to notify the Alliance Central Office, the Study Chair, and their Institutional Review Board if a patient has an adverse event requiring expedited reporting. The descriptions and grading scales found in the revised NCI Common Terminology Criteria for Adverse Events (CTCAE) version 5.0 will be utilized for AE reporting beginning April 1, 2018. All appropriate treatment areas should have access to a copy of the CTCAE version 5.0. A copy of the CTCAE version 5.0 can be downloaded from the CTEP web site

The Alliance requires investigators to route all expedited adverse event reports through the Alliance Central Protocol Operations Program Office for Alliance-coordinated studies.

Be sure to read this entire protocol section, as requirements are described in both the table and bullet points following the table. Note that the table below and the additional instructions or exclusions are protocol specific, and in the case of a conflict, the additional instructions or exclusions supersede the table.

9.3.1 Expedited Reporting Requirements for Adverse Events that Occur in a Non-IND/IDE trial \leq 30 Days of the Last Day of Treatment¹.

FDA REPORTING REQUIREMENTS FOR SERIOUS ADVERSE EVENTS (21 CFR Part 312)

NOTE: Investigators **MUST** immediately report to the sponsor (NCI) **ANY** Serious Adverse Events, whether or not they are considered related to the investigational agent(s)/intervention (21 CFR 312.64)

An adverse event is considered serious if it results in **ANY** of the following outcomes:

- 1) Death
- 2) A life-threatening adverse event
- 3) An adverse event that results in inpatient hospitalization or prolongation of existing hospitalization for \geq 24 hours
- 4) A persistent or significant incapacity or substantial disruption of the ability to conduct normal life functions
- 5) A congenital anomaly/birth defect.
- 6) Important Medical Events (IME) that may not result in death, be life threatening, or require hospitalization may be considered serious when, based upon medical judgment, they may jeopardize the patient or subject and may require medical or surgical intervention to prevent one of the outcomes listed in this definition. (FDA, 21 CFR 312.32; ICH E2A and ICH E6).

ALL SERIOUS adverse events that meet the above criteria **MUST** be immediately via CTEP-AERS within the timeframes detailed in the table below.

Hospitalization	Grade 1 Timeframes	Grade 2 Timeframes	Grade 3 Timeframes	Grade 4 & 5 Timeframes
-----------------	-----------------------	-----------------------	-----------------------	---------------------------

Resulting in Hospitalization \geq 24 hrs	10 Calendar Days		24-Hour; 5 Calendar Days
Not resulting in Hospitalization \geq 24 hrs	Not required	10 Calendar Days	

Expedited AE reporting timelines are defined as:
 
 ○ “24-Hour; 5 Calendar Days” - The AE must initially be reported via CTEP-AERS \leq 24 hours of learning of the AE, followed by a complete expedited report \leq 5 calendar days of the initial 24-hour report. ○ “10 Calendar Days” - A complete expedited report on the AE must be submitted \leq 10 calendar days of learning of the AE. 			

¹ Serious adverse events that occur more than 30 days after the day of treatment require reporting as follows:

Expedited 24-hour notification followed by complete report \leq 5 calendar days for:

- All Grade 4, and Grade 5 AEs that are at least possibly related to treatment

Expedited 10 calendar day reports for:

- Grade 2 adverse events resulting in hospitalization or prolongation of hospitalization and that are at least possibly related to treatment
- Grade 3 adverse events and that are at least possibly related to treatment

Additional Instructions or Exclusions:

- All adverse events reported via CTEP-AERS (i.e., serious adverse events) should also be forwarded to your local IRB, according to local IRB policies.
- Death due to progressive disease should be reported as Grade 5 “Disease progression” in the system organ class (SOC) “General disorders and administration site conditions.” Evidence that the death was a manifestation of underlying disease (e.g., radiological changes suggesting tumor growth or progression: clinical deterioration associated with a disease process) should be submitted.
- Treatment expected adverse events include those listed in [Section 10.0](#), in the package inserts for everolimus and sorafenib, and in the CAEPR for sorafenib. NOTE: The ASAEL column of the sorafenib CAEPR has been replaced with the specific protocol exceptions to expedited reporting (SPEER) list. This list now includes ‘expected’ severity grades in addition to event terms.
- All new malignancies must be reported through CTEP-AERS whether or not they are thought to be related to either previous or current treatment. All new malignancies should be reported, i.e. solid tumors (including non-melanoma skin malignancies), hematologic malignancies, myelodysplastic syndrome (acute myelogenous leukemia, and in situ tumors. In CTCAE v5.0, secondary malignancies may be reported as one of the following three options: 1) Leukemia secondary to oncology chemotherapy, 2) Myelodysplastic syndrome, or 3) Treatment-related secondary malignancy. Whenever possible, the CTEP-AERS reports for new malignancies should include tumor pathology, history or prior tumors, prior treatment/current treatment including duration, any associated risk factors or evidence regarding how long the new malignancy may have been present, when and how the new malignancy was detected, molecular characterization or cytogenetics of the original tumor (if available) and of any new tumor, and new malignancy treatment and outcome, if available.

- All pregnancies and suspected pregnancies occurring in female patients during therapy or within 28 days after completion of treatment on A091302 must be reported via CTEP-AERS. In CTCAE version 5.0, pregnancy loss is defined as “Death in utero,” and any pregnancy loss should be reported as “Pregnancy loss” under the Pregnancy, puerperium and perinatal conditions SOC (grade 4).
 - CTEP-AERS reports should be amended upon completion of the pregnancy to report pregnancy outcome (e.g. normal, spontaneous abortion, therapeutic abortion, fetal death, congenital abnormalities). Fetal deaths should be reported as “Death neonatal” under the General disorders and administration SOC (grade 4).
 - The CTEP-AERS report should be amended for any neonatal deaths occurring within 28 days of birth considered at least possibly related to treatment. Use the event term “Death neonatal” under the General disorders and administration SOC (grade 4).
- The reporting of adverse events described in the table above is in addition to and does not supplant the reporting of adverse events as part of the report of the results of the clinical trial, e.g. cooperative group data reporting.

